4.1.2 Exclusion Criteria

1. History of known leptomeningeal involvement (lumbar puncture not required).
2. Previous stereotactic or highly conformal radiotherapy within 1 weeks before the start of dosing for this study. **Note:** The stereotactic radiotherapy field must not have included the brain index lesion(s).
3. Subjects previously treated with SRT > 5 lesions in the brain.
4. Brain lesion size > 3 cm.
5. Prior checkpoint inhibitor therapy (which may include molecularly-targeted agents, IFN- α , and ipilimumab):
 - Patients who received ipilimumab as adjuvant or neoadjuvant therapy must have a 6-month washout before receiving any dosing on this study.
 - Cohort A: Prior anti-PD1 in the adjuvant setting is allowed, but patients must not have progressed within six months of the last dose of adjuvant therapy.
 - Cohort B: Patients with unresectable metastatic melanoma who received either anti-PD-1 or PDL-1 in the past are eligible. Washout period a minimum 3 weeks.
6. Subjects with an active, known or suspected autoimmune disease. Subjects with type I diabetes mellitus, hypothyroidism only requiring hormone replacement, skin disorders (such as vitiligo, psoriasis, or alopecia) not requiring systemic treatment, or conditions not expected to recur in the absence of an external trigger are permitted to enroll.
7. Subjects with major medical, neurologic or psychiatric condition who are judged as unable to fully comply with study therapy or assessments should not be enrolled.
8. Subject has a history of a second malignancy, unless potentially curative treatment has been completed with no evidence of malignancy for 2 years. Note: The time requirement does not apply to participants who underwent successful treatment of superficial bladder cancer, in situ cervical cancer, or other in-situ cancers. Subjects with a completely treated prior malignancy and no evidence of disease for ≥ 2 years are eligible.
 - a. Skin Cancer Exclusion: Please note that basal cell carcinoma and squamous cell carcinoma is exempt from needing resection prior to treatment. (Resection can be completed after the start of treatment).
9. Has a known history of or is positive for hepatitis B (hepatitis B surface antigen [HBsAg] reactive) or hepatitis C (hepatitis C virus [HCV] RNA [qualitative] is detected).
 - a. **Note:** Without known history, testing needs to be performed to determine eligibility. Hepatitis C antibody (Ab) testing is allowed for screening purposes in countries where HCV RNA is not part of standard of care.

Proprietary Information of MD Anderson

10. Has a known history of human immunodeficiency virus (HIV) infection. No HIV testing is required unless mandated by local health authority.
11. The use of corticosteroids is not allowed for 10 days prior to initiation of therapy (based upon 5 times the expected half-life of dexamethasone) except patients who are taking steroids for physiological replacement. If alternative corticosteroid therapy has been used, consultation with the PI is required to determine the washout period prior to initiating study treatment.
12. Subjects with a condition requiring systemic treatment with either corticosteroids (> 10 mg daily prednisone equivalent) or other immunosuppressive medications within 14 days of study initiation. Inhaled or topical steroids, and adrenal replacement steroid doses > 10 mg daily prednisone equivalent, are permitted in the absence of active autoimmune disease.
13. Subjects with history of life-threatening toxicity related to prior ipilimumab adjuvant therapy except those that are unlikely to re-occur with standard countermeasures (e.g. hormone replacement after adrenal crisis)
14. Major surgical procedure, open biopsy (excluding skin cancer resection), or significant traumatic injury within 14 days of initiating study drug (unless the wound has healed) or anticipation of the need for major surgery during the study.
15. Non-healing wound, ulcer, or bone fracture.
16. Women who are breast-feeding or pregnant.
17. Uncontrolled intercurrent illness (i.e., active infection \geq grade 2) or concurrent condition that, in the opinion of the Investigator, would interfere with the study endpoints or the subject's ability to participate.
18. History of clinically significant cardiac disease or congestive heart failure $>$ New York Heart Association (NYHA) class 2. Subjects must not have unstable angina (anginal symptoms at rest) or new-onset angina within the last 3 months or myocardial infarction within the past 6 months.
19. Investigational drug use within 14 days (or 5 half-lives, whichever is longer) of the first dose of ipilimumab and pembrolizumab.
20. Has a history of non-infectious pneumonitis that required steroids or current pneumonitis.

4.2

TRIAL TREATMENTS

Treatment will consist of 3-week cycles and will continue until documented disease progression, unacceptable AEs, intercurrent illness that prevents further administration of treatment, investigator's decision to withdraw the subject, subject withdraws consent, pregnancy of the subject, noncompliance with trial treatment or procedure requirements, completion of 35 doses of treatment with pembrolizumab, or administrative reasons.

Pembrolizumab is to be administered first when in combination with Ipilimumab.

Proprietary Information of MD Anderson

Table 2: Trial Treatments and Description

Product	Dose	Dose Frequency	Route of Administration	Appearance	Storage Conditions (per label)
Ipilimumab	1mg/kg	Every 3 Weeks for up to 4 doses	IV Infusion	Clear, colorless to pale yellow liquid. May contain particles	2°C to 8°C. Protect from light and freezing
Pembrolizumab	200 mg	Every 3 Weeks (up to 35 doses)	IV Infusion		

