12. Women of child-bearing potential (WOCBP) must not be breastfeeding and must have a negative pregnancy test within 3 days prior to initiation of dosing. She must agree to use an acceptable method of birth control from the time of the negative pregnancy test up to 120 days after the last dose of study drug. WOCBP must agree to adhere to the contraceptive guidance in Appendix 5. **Note:** A female participant is eligible to participate if she is not a woman of childbearing potential as defined in Appendix 5.

Proprietary Information of MD Anderson

13. Fertile men must agree to use an acceptable method of birth control as described in Appendix 5 while on study drug and up to 120 days after the last dose of study drug and also refrain from donating sperm during this period.
14. All associated toxicity from previous or concurrent cancer therapy must be resolved (to ≤ grade 1 or baseline) prior to study treatment administration. This excludes non-serious toxicities.
15. Steroids for physiological replacement are allowed.

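### Exclusion 13 bars past life-threatening toxicity only from adjuvant ipilimumab, so most resolved Grade 4 events from prior anti-PD-1/PD-L1 or neoadjuvant ipilimumab do not prevent entry

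*Combined protocol and SAP*

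**What the plan says.** The bar on past life-threatening toxicity is exclusion 13 in Section 4.1.2: "Subjects with history of life-threatening toxicity related to prior ipilimumab adjuvant therapy except those that are unlikely to re-occur with standard countermeasures". The exception is illustrated by hormone replacement after adrenal crisis.

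Exclusion 5 in the same section lets in a wider set of checkpoint-inhibitor histories:

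- **Ipilimumab before or after surgery:** "Patients who received ipilimumab as adjuvant or neoadjuvant therapy must have a 6-month washout before receiving any dosing on this study".
- **Cohort A:** "Cohort A: Prior anti-PD1 in the adjuvant setting is allowed". The only condition is that the disease did not progress within six months of the last adjuvant dose.
- **Cohort B:** "Cohort B: Patients with unresectable metastatic melanoma who received either anti-PD-1 or PDL-1 in the past are eligible". The only condition is a washout of at least 3 weeks.

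None of these entries asks how the earlier drug was tolerated. Section 3 gives every patient the same induction: pembrolizumab 200 mg with ipilimumab 1 mg/kg every 3 weeks for up to four doses.

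**The concern.** The safety bar is narrower than the set of prior treatments admitted. Exclusion 5 names adjuvant and neoadjuvant ipilimumab together, whereas exclusion 13 names only adjuvant. Neither anti-PD-1 nor anti-PD-L1 appears in exclusion 13, although pembrolizumab is the study drug given for longest (up to 35 doses, against up to 4 of ipilimumab).

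What is at stake is patient safety. Applied as written, the criteria could re-expose a patient to the drug class that caused a life-threatening event, this time in combination. Section 4.2.2 itself warns that toxicities common to the two drugs may be made worse when they are given together. The primary endpoint, the power and the analysis are not affected.

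**Working it through.** No figure in the plan can be reproduced here, because the point rests on the wording of the criteria. The check has two steps.

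**Step 1. Does any other criterion catch the patient?** Take a patient with a resolved Grade 4 colitis, hepatitis or nephritis from earlier anti-PD-1/PD-L1, or from neoadjuvant ipilimumab more than 6 months ago. Table 9 defines Grade 4 by life-threatening consequences, so the event is of the severity exclusion 13 addresses. The criteria that might apply are:

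| Criterion | What it tests | Catches the patient? |
|---|---|---|
| Inclusion 14 | "All associated toxicity from previous or concurrent cancer therapy must be resolved" to Grade 1 or baseline; no limit on the worst past grade | No, the event has resolved |
| Exclusion 6 | Autoimmune disease, but "conditions not expected to recur in the absence of an external trigger are permitted to enroll" | Not on its wording |
| Exclusion 7 | Inability to comply with therapy or assessments | No |
| Exclusion 12 | Need for systemic immunosuppression within 14 days of starting | No, once treatment for the event has ended |
| Exclusion 17 | Current illness or concurrent condition, partly at the investigator's discretion | No, the event is past |
| Exclusion 18 | "History of clinically significant cardiac disease or congestive heart failure" above a stated class | Possibly myocarditis, nothing else here |
| Exclusion 20 | "Has a history of non-infectious pneumonitis that required steroids or current pneumonitis" | Pneumonitis only |

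None requires this patient to be excluded.

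**Step 2. How does the protocol treat the same event on study?** Counting the immune-related rows of Table 3 (Section 4.2.2.1) by the action required at Grade 4:

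- Permanently discontinue: 7 (pneumonitis, diarrhea/colitis, liver tests, nephritis, neurological, myocarditis, all other immune-related events).
- Withhold or permanently discontinue, at discretion: 2 (hypophysitis, hyperthyroidism).
- Withhold: 1 (type 1 diabetes/hyperglycemia).
- Continue: 1 (hypothyroidism).
- Decided by diagnosis and not by grade: 1 (exfoliative skin conditions).

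Total: 7 + 2 + 1 + 1 + 1 = 12.

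Of the 7, exclusion 20 covers pneumonitis (when current or treated with steroids) and exclusion 18 may cover myocarditis: 7 − 1 − 1 = 5. Colitis, liver, nephritis, neurological and all other immune-related events thus have no matching bar at entry. Table 4 adds one more, since a Grade 4 infusion reaction ends dosing. The count is conservative. Confirmed SJS, TEN or DRESS also ends pembrolizumab, but that row is left out because it is not graded.

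Grade 3 events are outside this point, because Table 9 describes them as not immediately life-threatening.

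**The case against.** The case against accepts this reading of exclusion 13 and the row count, and contests how much follows from them.

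- **Cohort B is defined by progression on a PD-1 inhibitor (Section 3).** A patient who stopped for toxicity without progressing does not clearly fit, which narrows the group, and the cohort has only 5 of the 30 places. This stands in part. However, toxicity and progression can occur in the same patient, and the definition does nothing for Cohort A, where up to 25 patients may have had adjuvant anti-PD-1. There is no basis for saying in which cohort the affected patients would mostly fall.
- **The sponsor has made no judgement on anti-PD-1 re-exposure.** Correct: exclusion 13 speaks only of ipilimumab, and extending it is an inference. The inference rests on Tables 3 and 4, where the protocol ends pembrolizumab for the same Grade 4 events. No reason is given for the narrower wording.
- **The rechallenge note in Table 9 requires advance approval where re-exposure poses significant added risk.** Read alone, that limb could reach a patient whose earlier event was on pembrolizumab. But it sits in the table for judging adverse-event causality, under a question about re-exposure in this study. It screens no one at entry and covers other anti-PD-1 products less clearly.
- **Exclusion 6 could be applied.** An investigator might say that the study treatment is itself the external trigger and refuse the exemption. That is an available reading, but the text as written permits entry.
- **On-study safeguards exist.** Section 4.2.2 stops treatment when the same serious event recurs at the same or a higher grade on rechallenge, and safety is reviewed monthly at the single site. These act after exposure, and the first acts only after recurrence.
- **The amended rule keeps an undefined exception.** True. Entry would still involve judgement, for example over premedication after a past infusion reaction.

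**Conclusion.** The concern holds. As written, the criteria admit patients with a resolved Grade 4 event from prior anti-PD-1/PD-L1 or neoadjuvant ipilimumab, except steroid-treated or current pneumonitis and possibly myocarditis. Five of the 7 Table 3 rows with a mandatory permanent stop at Grade 4, plus the Grade 4 infusion reaction, have no entry counterpart.

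That figure counts rules and measures neither patients nor risk. The documents do not say how many patients are affected, and the number could be zero. Investigators remain free not to enrol such a patient, but no criterion obliges them to refuse, and for adjuvant ipilimumab the protocol did not leave the matter to discretion. The conclusion assumes that life-threatening in exclusion 13 means Grade 4, as Table 9 describes that grade. It should be fixed because the change is cheap and concerns safety.

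**What to change.** Reword exclusion 13 along these lines: *history of life-threatening (Grade 4) toxicity related to any prior checkpoint inhibitor (ipilimumab, anti-PD-1 or anti-PD-L1, in any setting)*, followed by the existing exception for events that standard countermeasures make unlikely to return. The exception is worth keeping because it fits Table 3: the 4 graded rows without a mandatory permanent stop at Grade 4 are all endocrine (type 1 diabetes/hyperglycemia, hypophysitis, hyperthyroidism, hypothyroidism).

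Whether also to bar past Grade 2 or 3 events that Table 3 treats as grounds for permanent discontinuation is a separate decision for the sponsor and is not needed here.

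The cost is a one-line eligibility amendment and possibly a few screen failures; their number is unknown and may be zero.

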4.2.1 Dose Selection

The dose for pembrolizumab is based on the current FDA approved label; the ipilimumab dose is based on clinical research data from KEYNOTE-029 (1mg/kg every 3 weeks, for up to 4 doses). Refer to Section 1.2 for clinical trial details.

4.2.2 Dose Modification

Dose reductions or dose escalations are not permitted.

Toxicities common to ipilimumab and pembrolizumab include, but are not limited to rash, endocrinopathy, hepatotoxicity, diarrhea, and pneumonitis. Therefore, it is possible that these and/or other toxicities may be exacerbated when pembrolizumab is given in combination with ipilimumab.

Subjects who experience an unacceptable toxicity that is attributed to ipilimumab in the opinion of the Investigator, may permanently discontinue ipilimumab, but may continue with pembrolizumab, upon resolution of toxicity to Grade 0-1 or baseline, until unacceptable toxicity or progression. Subjects who discontinue pembrolizumab due to untoward toxicities may not continue on the trial receiving only ipilimumab.

For subjects who experience a recurrence of the same AE(s) at the same Grade or greater with rechallenge of study treatment(s), the Investigator should determine whether the subject should continue on the trial. However, for a subject who experiences a recurrence of the same SAE at the same Grade or greater with rechallenge, the subject must discontinue trial treatment.

Investigators should refer to the appropriate IB/label for pembrolizumab and/or ipilimumab for additional information regarding the background of each drug and the management of other AEs or potential safety-related issues. Dosing interruptions are permitted in the case of medical/surgical events or logistical reasons not related to trial therapy (e.g., elective surgery, unrelated medical events, subject vacation, and/or holidays). Subjects should be placed back on trial therapy within 3 weeks of the scheduled interruption, unless otherwise decided by the Investigator. The reason for interruption should be documented in the subject's trial record.

Proprietary Information of MD Anderson

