4.2.2.1 Pembrolizumab Dose Modifications

See the table below for Dose Modification guidelines for pembrolizumab.

Table 3: Dose modification and toxicity management guidelines for immune-related AEs associated with pembrolizumab monotherapy and IO Combinations

General instructions:
 
 1. Severe and life-threatening irAEs should be treated with IV corticosteroids followed by oral steroids. Other immunosuppressive treatment should begin if the irAEs are not controlled by corticosteroids. 2. Study intervention must be permanently discontinued if the irAE does not resolve or the corticosteroid dose is not \leq10 mg/day within 12 weeks of the last study intervention treatment. 3. The corticosteroid taper should begin when the irAE is \leq Grade 1 and continue at least 4 weeks. 4. If study intervention has been withheld, study intervention may resume after the irAE decreased to \leq Grade 1 after corticosteroid taper. 				
--	--	--	--	--

irAEs	Toxicity Grade (CTCAE v5.0)	Action With Pembrolizumab	Corticosteroid and/or Other Therapies	Monitoring and Follow-up
Pneumonitis	Grade 2	Withhold	
 • Administer corticosteroids (initial dose of 1 to 2 mg/kg prednisone or equivalent) followed by taper 	
 • Monitor participants for signs and symptoms of pneumonitis
	Recurrent Grade 2, Grade 3 or 4	Permanently discontinue	
 • Add prophylactic antibiotics for opportunistic infections 	
 • Evaluate participants with suspected pneumonitis with radiographic imaging and initiate corticosteroid treatment
Diarrhea/Colitis	Grade 2 or 3	Withhold	
 • Administer corticosteroids (initial dose of 1 to 2 mg/kg prednisone or equivalent) followed by taper 	
 • Monitor participants for signs and symptoms of enterocolitis (ie, diarrhea, abdominal pain, blood or mucus in stool with or without fever) and of bowel perforation (ie, peritoneal signs and ileus)
	Recurrent Grade 3 or Grade 4	Permanently discontinue		
 • Participants with \geqGrade 2 diarrhea suspecting colitis should consider GI consultation and performing endoscopy to rule out colitis

irAEs	Toxicity Grade (CTCAE v5.0)	Action With Pembrolizumab	Corticosteroid and/or Other Therapies	Monitoring and Follow-up

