Nephritis: grading according to increased creatinine or acute kidney injury	Grade 2	Withhold	
 Administer corticosteroids (prednisone 1 to 2 mg/kg or equivalent) followed by taper 	
 Monitor changes of renal function
	Grade 3 or 4	Permanently discontinue		
Neurological Toxicities	Grade 2	Withhold	
 Based on severity of AE administer corticosteroids 	
 Ensure adequate evaluation to confirm etiology and/or exclude other causes
	Grade 3 or 4	Permanently discontinue		
Myocarditis	Grade 1	Withhold	
 Based on severity of AE administer corticosteroids 	
 Ensure adequate evaluation to confirm etiology and/or exclude other causes
	Grade 2, 3 or 4	Permanently discontinue		
Exfoliative Dermatologic Conditions	Suspected SJS, TEN, or DRESS	Withhold	
 Based on severity of AE administer corticosteroids 	
 Ensure adequate evaluation to confirm etiology or exclude other causes
	Confirmed SJS, TEN, or DRESS	Permanently discontinue		
All Other irAEs	Persistent Grade 2	Withhold	
 Based on severity of AE administer corticosteroids 	
 Ensure adequate evaluation to confirm etiology or exclude other causes
	Grade 3	Withhold or discontinue based on the event ^e		
	Recurrent Grade 3 or Grade 4	Permanently discontinue		

^aAE(s)=adverse event(s); ALT= alanine aminotransferase; AST=aspartate aminotransferase; CTCAE=Common Terminology Criteria for Adverse Events; DRESS=Drug Rash with Eosinophilia and Systemic Symptom; GI=gastrointestinal; IO=immuno-oncology; ir=immune related; IV=intravenous; SJS=Stevens-Johnson Syndrome; T1DM=type 1 diabetes mellitus; TEN=Toxic Epidermal Necrolysis; ULN=upper limit of normal.

Note: Non-irAE will be managed as appropriate, following clinical practice recommendations.

irAEs	Toxicity Grade (CTCAE v5.0)	Action With Pembrolizumab	Corticosteroid and/or Other Therapies	Monitoring and Follow-up
^a				
^a			AST/ALT: >3.0 to 5.0 x ULN if baseline normal; >3.0 to 5.0 x baseline, if baseline abnormal; bilirubin: >1.5 to 3.0 x ULN if baseline normal; >1.5 to 3.0 x baseline if baseline abnormal	
^b				

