^b				AST/ALT: >5.0 to 20.0 x ULN, if baseline normal; >5.0 to 20.0 x baseline, if baseline abnormal; bilirubin: >3.0 to 10.0 x ULN if baseline normal; >3.0 to 10.0 x baseline if baseline abnormal
^c				
^c				AST/ALT: >20.0 x ULN, if baseline normal; >20.0 x baseline, if baseline abnormal; bilirubin: >10.0 x ULN if baseline normal; >10.0 x baseline if baseline abnormal
^d				The decision to withhold or permanently discontinue pembrolizumab is at the discretion of the investigator or treating physician. If control achieved or ≤ Grade 2, pembrolizumab may be resumed.
^e				Events that require discontinuation include, but are not limited to: encephalitis and other clinically important irAEs (eg, vasculitis and sclerosing cholangitis).

Dose modification and toxicity management of infusion-reactions related to pembrolizumab

Pembrolizumab may cause severe or life threatening infusion-reactions including severe hypersensitivity or anaphylaxis. Signs and symptoms usually develop during or shortly after drug infusion and generally resolve completely within 24 hours of completion of infusion. Dose modification and toxicity management guidelines on pembrolizumab associated infusion reaction are provided in

When study interventions are administered in combination, attribution of an adverse event to a single component is likely to be difficult. Therefore, while the investigator may attribute a toxicity event to Pembrolizumab or combination, For adverse events listed, both interventions must be held according to the criteria in the Dose Modification and Toxicity Management Guidelines for Immune-Related Adverse Events Associated with Pembrolizumab table.

Holding Study Interventions:

When study interventions are administered in combination, if the AE is considered immune-related, both interventions should be held according to recommended dose modifications.

Restarting Study Interventions:

Participants may not have any dose modifications (no change in dose or schedule) of pembrolizumab in this study, as described in [Table 6].

If the toxicity does not resolve or the criteria for resuming treatment are not met, the participant must be discontinued from all study interventions.

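### Section 4.2.2 lets pembrolizumab continue, or leaves recurrence to judgement, in cases where Table 3 requires permanent discontinuation, and no text says which governs

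*Combined protocol and SAP*

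**What the plan says.** Section 4.2.2 (Dose Modification) contains two general rules.

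- Attribution: a subject with an unacceptable toxicity that the investigator attributes to ipilimumab "may permanently discontinue ipilimumab, but may continue with pembrolizumab, upon resolution of toxicity to Grade 0-1 or baseline". No event, peak grade or time limit is given, and Table 3 is not mentioned.
- Recurrence: if the same AE returns at the same or a higher grade on rechallenge, "the Investigator should determine whether the subject should continue on the trial". A recurrent SAE, by contrast, is a mandatory stop, so the discretion covers non-serious recurrences only.

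Table 3 (Section 4.2.2.1) is titled to cover "immune-related AEs associated with pembrolizumab monotherapy and IO Combinations". It acts on event and grade and has no attribution column. Its action for pembrolizumab is permanent discontinuation in eight categories:

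- pneumonitis, "Recurrent Grade 2, Grade 3 or 4";
- diarrhea/colitis and all other irAEs, each "Recurrent Grade 3 or Grade 4";
- hepatic, renal and neurological events at Grade 3 or 4;
- myocarditis at Grade 2, 3 or 4;
- exfoliative conditions, "Confirmed SJS, TEN, or DRESS".

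Grade 3 events in the all-other category are withheld or discontinued according to the event; footnote e says: "Events that require discontinuation include, but are not limited to: encephalitis and other clinically important irAEs".

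General instruction 2 requires permanent discontinuation if, within 12 weeks of the last treatment, the irAE has not resolved or the steroid dose is not down to 10 mg/day. General instruction 4 gives the way back: "If study intervention has been withheld, study intervention may resume after the irAE decreased to" Grade 1 or lower after the taper.

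**The concern.** Both rules tell the investigator what to do with pembrolizumab after an immune-related event, and in some cases they differ. Section 4.2.2 opens its permission on a causality judgement, whereas Table 3 ignores causality. The text after Table 3 itself warns that assigning an event to one of two drugs given together is likely to be difficult. An investigator acting in good faith on the Section 4.2.2 permission could therefore restart pembrolizumab in a patient whom Table 3 bars from it. The stake is patient safety. The primary analysis is not affected.

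**Working it through.** The point rests on the wording, so no arithmetic applies. The steps set the two rules against the same cases.

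**Step 1: do the rules reach the same events?** Yes. Section 4.2.2 speaks of unacceptable toxicity rather than irAEs, but the toxicities it lists as common to both drugs include hepatotoxicity, diarrhea and pneumonitis, which are Table 3 categories.

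**Step 2: apply both rules to four cases.**

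| Case | Section 4.2.2 | Table 3 |
|---|---|---|
| Grade 3 ALT elevation, attributed to ipilimumab, resolves to Grade 1 | Pembrolizumab may continue | Permanently discontinue |
| Grade 2 myocarditis, attributed to ipilimumab, resolves to baseline | Pembrolizumab may continue | Permanently discontinue |
| Grade 2 pneumonitis, withheld, resumed, recurs at Grade 2, non-serious | Investigator decides | Permanently discontinue |
| Grade 2 hepatic event, attributed to ipilimumab, reaches Grade 1 only after more than 12 weeks | Pembrolizumab may continue | Permanently discontinue (instruction 2) |

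The third case does not depend on attribution. Recurrent Grade 3 colitis and recurrent Grade 3 other irAEs raise the same question, but many of those would probably be serious and so stopped under both rules. Recurrent Grade 2 pneumonitis is the clearest example. The fourth case shows that the mismatch is not confined to the rows marked for permanent discontinuation, because instruction 2 can force a stop from a row that begins with withholding. Footnote d runs the other way: it allows pembrolizumab to resume with control or at Grade 2 or less, where Section 4.2.2 asks for Grade 0-1 or baseline.

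**Step 3: does other text settle it?** The paragraphs after Table 3 lean to the table.

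- One sentence says that for listed events both drugs must be held by the table's criteria. Its attribution clause names pembrolizumab or the combination, not ipilimumab alone.
- The paragraph headed Holding Study Interventions has no attribution test: during combination dosing, any AE considered immune-related leads to both drugs being held according to the recommended modifications. An ipilimumab-attributed irAE falls within it.
- Under Restarting Study Interventions, all treatment stops if resume criteria are not met. Read with instruction 4, which provides for resumption only of withheld treatment, a permanent-discontinuation row has no route back.

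Three gaps remain. This text speaks of holding, not of permanent discontinuation. It does not address recurrence. It does not say that it overrides Section 4.2.2. The restart paragraph also makes resumption depend on conditions that it does not name, because the sentence is incomplete, and then offers pembrolizumab monotherapy at the principal investigator's discretion.

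**Step 4: what safeguards exist?** Section 7.1 assigns causality to the combination by default and allows single-agent attribution only with sufficient supporting data. The rechallenge note in Table 9 requires advance IND Office approval after a serious event that the Merck product may have caused, or where re-exposure adds potentially significant risk; the second condition does not depend on attribution. Section 4.2.3 requires the PI to be consulted before treatment restarts after an interruption of more than 6 weeks. None of these says which rule prevails.

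**The case against.** The best case for the plan is that this is a general permission followed by a specific limit. Table 3 sits in a sub-section of Section 4.2.2, its actions are specific to event and grade, and the Section 4.2.2 option is only permissive. The attribution-free holding paragraph, instruction 4 and the stop rule together come close to answering the attribution question in favor of Table 3. The rechallenge note ties approval to the protocol's dose modification guidelines, a phrase that Section 4.2.2.1 uses to introduce Table 3. The recurrence discretion is confined to non-serious events on rechallenge, and a general direction to decide is not leave to disregard the table. Exposure is also limited: one site, 30 subjects, at most four ipilimumab doses during induction, and monthly safety review.

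Most of this stands, and it rules out several stronger readings.

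- A reader might infer that an investigator cannot comply with both rules. That is not so, because stopping pembrolizumab satisfies both.
- A reader might take the monotherapy sentence as free-standing discretion to restart after any event. Its wording refers back to toxicities that have resolved with the conditions met. The defect is that those conditions are unnamed.
- A reader might take Section 4.5 to confine Table 3 to pembrolizumab-related events. Its relatedness condition concerns supportive care and does not set the dosing rule.

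The objection does not remove the core point. The harmonized reading has to be assembled from several paragraphs, it leaves recurrence unaddressed, and the permission in Section 4.2.2 remains unqualified on its face.

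**Conclusion.** The inconsistency is real and should be fixed. In eight irAE categories, and under the 12-week instruction, Section 4.2.2 can permit or leave open what Table 3 forbids. The surrounding text favors Table 3 without expressly resolving the matter. The hazard arises only when an investigator uses the permission or the discretion; the safeguards reduce it but do not reconcile the rules.

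The number of patients affected cannot be derived. The documents do not give the frequency of the conflicting events or how often they would be attributed to ipilimumab alone. Section 1.2 reports Grade 3 and 4 toxicity in 45% of 153 patients on a similar regimen. That makes severe events foreseeable, but it should not be read as the rate of this conflict. Counting table rows would not measure risk either. There is no effect on power or error rates. The conclusion assumes only that Section 4.2.2 and Table 3 are both meant to be in force for the combination, as the table's title indicates.

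**What to change.** - In Section 4.2.2, state that the ipilimumab-attribution option and the recurrence discretion are both subject to Table 3, including general instruction 2, and do not apply where Table 3 requires permanent discontinuation.
- Under Restarting Study Interventions, replace the incomplete phrase about conditions with the Table 3 resume criteria, and limit monotherapy re-initiation to events that Table 3 allows to be withheld.
- Name any deliberate exception, for example a defined event after which pembrolizumab may continue when ipilimumab is judged the sole cause. Whether to allow one is a clinical decision for the sponsor and the investigator.

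The cost is a few sentences of protocol wording and retraining at one site, with no new procedures. The downside is less investigator discretion: a patient whose toxicity truly came from ipilimumab alone may lose pembrolizumab unless an exception is named.
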